AE/SAE monitoring	X	X	X	X	X	X	X	X	X	X		Report AEs occurring within 30 days after the last dose of study intervention. Report SAEs occurring within 90 days after the last dose of study intervention, or 30 days after the last dose of study intervention if a new anticancer therapy is initiated, whichever is earlier.
Subsequent antineoplastic therapy status								X	X	X	X	All anticancer therapy will be recorded until time of death or termination of Survival Follow-up. If a clinic visit is not feasible, follow-up information may be obtained via documented contact.
Survival status		←————→									X	Refer to Sections 8.11.5.3 & 8.11.6. Updated survival status may be requested by the Sponsor at any time during the course of the study.
Imaging												
Brain imaging	X											Required for all participants at screening. See Section 8.2.1.2 for other requirements. If MRI is contraindicated or cannot be performed, CT of the head with IV contrast is acceptable.
Bone imaging	X											Required at screening for participants with history of bone metastases. See Section 8.2.1.2 for other requirements.

Study Period	Screening	Treatment Cycle = 21 Days						EOT	Post-treatment			Notes
		1	2	3	4	5	6 to 35		Safety Follow-up	Efficacy Follow-up	Survival Follow-up	
Visit Timing / Cycle Number	-28 to -1	1	1	1	1	1	1	At DC	30 Days post last dose	Every 12 weeks	Every 12 weeks	All procedures are to be performed before study intervention administration unless otherwise indicated. Refer to Section 8.11 for visit details.
Cycle Day		1	1	1	1	1	1	–				
Scheduling Window (Days)		+3	±3	±3	±3	±3	±3		+14	±7	±14	
Tumor imaging and response assessment (chest, abdomen, and pelvis)	X			X				X		X		Schedule should be followed regardless of treatment delays. Perform imaging at Screening, then Q9W (63 ±7 days) from randomization through Week 54, and Q12W (±7 days).thereafter until BICR confirmed PD or initiation of a new anticancer regimen. If imaging was obtained within 4 weeks before treatment DC, scan at DC is not mandatory. Follow-up visits may be scheduled to coincide with the imaging schedule. Note: On-study brain or bone imaging should be performed if clinically indicated or to confirm CR (if other lesions indicate CR and brain or bone lesions existed at baseline).
Laboratory Assessments												
Pregnancy test for WOCBP	X	X	X	X	X	X	X	X	X			WOCBP require negative serum test within 72 hours or negative urine test within 24 hours prior to each dose of study intervention.

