### 1.3.2 Second Course Treatment Phase

Table 2 Study Schedule of Activities – Second Course Treatment Phase

Study Period:	Treatment Cycle = 21 days						End of Treatment	Post-Treatment			Notes
Visit Timing / Cycle Number	1	2	3	4	5	6 to 17	At DC	Safety Follow-up	Efficacy Follow-up	Survival Follow-up	Procedures within a given treatment visit should occur on Day 1 of each cycle unless otherwise noted.
								30 days post last dose	Every 12 weeks post-DC	Every 12 weeks	
Scheduling Window (Days):									+14	±7	
Administrative Procedures											
Eligibility Criteria	X										
Concomitant Medication Review	X	X	X	X	X	X	X	X			Concomitant medications received within 30 days before the first dose of study intervention in the Second Course through 30 days after the last dose of study intervention (or 90 days if used to treat an SAE) will be recorded.
Clinical Procedures/Assessments											
Review Adverse Events	X	X	X	X	X	X	X	X	X	X	Report AEs occurring within 30 days after the last dose of study intervention. Report SAEs occurring within 90 days after the last dose of study intervention, or 30 days after the last dose of study intervention if a new anticancer therapy is initiated, whichever is earlier.
Complete Physical Examination	X						X				
Directed Physical Examination		X	X	X	X	X		X			
Vital Signs and Weight	X	X	X	X	X	X	X	X			Pre-dose and if clinically indicated.

Study Period:	Treatment Cycle = 21 days						End of Treatment	Post-Treatment			Notes
	1	2	3	4	5	6 to 17	At DC	Safety Follow-up	Efficacy Follow-up	Survival Follow-up	
Visit Timing / Cycle Number								30 days post last dose	Every 12 weeks post-DC	Every 12 weeks	Procedures within a given treatment visit should occur on Day 1 of each cycle unless otherwise noted.
Scheduling Window (Days):		±3	±3	±3	±3	±3		+14	±7	±14	
ECOG Performance Status	X	X	X	X	X	X	X				Performed within 7 days of beginning of C1 and prior to each treatment administration.
Study Intervention Administration	X	X	X	X	X	X					
Poststudy Anticancer Therapy Status							X	X	X	X	
Survival Status	←-----→									X	Refer to Sections 8.11.5.3 & 8.11.6. Updated survival status may be requested by the Sponsor at any time during the course of the study.
Laboratory Procedures/Assessments											
Pregnancy Test for WOCBP	X	X	X	X	X	X	X	X			WOCBP require negative serum test within 72 hours or negative urine test within 24 hours prior to each dose of study intervention.

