## **6.6 Dose Modification (Escalation/Titration/Other)**

### **6.6.1 Immune-Related Events and Dose Modification (Withhold, Treat, Discontinue)**

#### **Dose Modification and Toxicity Management for Immune-related AEs Associated with Pembrolizumab Monotherapy, Coformulations or IO Combinations**

AEs associated with pembrolizumab monotherapy, coformulation, or IO combination exposure may represent an immune-related response. These irAEs may occur shortly after the first dose or several months after the last dose of pembrolizumab monotherapy, coformulation, or IO combination treatment and may affect more than one body system simultaneously. Therefore, early recognition and initiation of treatment is critical to reduce

complications. Based on existing clinical study data, most irAEs were reversible and could be managed with interruptions of pembrolizumab monotherapy, coformulation, or IO combination administration of corticosteroids and/or other supportive care. For suspected irAEs, ensure adequate evaluation to confirm etiology or exclude other causes. Additional procedures or tests such as bronchoscopy, endoscopy, skin biopsy may be included as part of the evaluation.

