#### **8.11.4 Participants Discontinued From Study Intervention but Continuing to be Monitored in the Study**

Participants who discontinue study treatment due to disease recurrence or start of a new anticancer therapy will have Safety Follow-up and then proceed directly to Survival Follow-up Phase as described in Section 8.11.5.

The Discontinuation Visit should occur at the time study intervention is discontinued for any reason. If the Discontinuation Visit occurs 30 days from the last dose of study intervention, at the time of the mandatory safety follow-up visit, the Discontinuation Visit procedures and any additional Safety Follow-up procedures should be performed.

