##### **8.11.5.3 Survival Follow-up Contacts**

Participant survival follow-up status will be assessed approximately every 12 weeks to assess for survival status until death, withdrawal of consent, or the end of the study, whichever occurs first.

The first survival follow-up assessment should be scheduled as described below:

- For participants who discontinue treatment intervention and who will not enter Efficacy Follow-up, the first survival follow-up contact will be scheduled 12 weeks after the Discontinuation Visit and/or Safety Follow-up Visit (whichever is last).
- For participants who completed assessments in Efficacy Follow-up, the first survival follow-up contact will be scheduled 12 weeks after the last efficacy assessment follow-up visit has been performed.

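### Table 1 schedules no SAE check after about day 30 for participants who stop for progression and start no new therapy, although their SAE window runs to day 90

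*Combined protocol and SAP*

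**What the plan says.** - **SAE window.** The note to the "AE/SAE monitoring" row of Table 1 (Section 1.3.1) reads "Report SAEs occurring within 90 days after the last dose of study intervention". It then makes an exception that shortens the window for some participants: "30 days after the last dose of study intervention if a new anticancer therapy is initiated, whichever is earlier". Section 8.4.1 sets the same rule.
- **Table 1 marks.** The row is marked from Screening through Efficacy Follow-up. The Survival Follow-up cell is blank.
- **Table 2 marks.** In the Second Course schedule (Section 1.3.2) the matching row, "Review Adverse Events", carries the same note and is marked in every column, including Survival Follow-up.
- **Routing.** Under Section 8.11.4, participants who stop for disease recurrence or new therapy "will have Safety Follow-up and then proceed directly to Survival Follow-up Phase". Section 8.11.5.2 keeps Efficacy Follow-up for those who complete treatment or stop for a reason other than progression.
- **Survival contact.** Section 8.11.5.3 states: "Participant survival follow-up status will be assessed approximately every 12 weeks to assess for survival status". Table 1 also marks subsequent anticancer therapy at this contact, but no AE item.
- **Late events.** Section 6.6.1 says that immune-related AEs "may occur shortly after the first dose or several months after the last dose".
- **Amendment 06** (repeated at the head of Sections 1, 4 and 6 to 9). Survival follow-up ends, and the Safety Follow-up Visit becomes the final required visit. Participants still on study are nevertheless to be monitored through the reporting period of Section 8.4.

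**The concern.** The reporting window and the visit schedule do not match for one group: participants who stop for progression and start no new therapy. Their window is open to day 90, but their last scheduled AE/SAE question comes at about day 30. Someone who stops for toxicity goes to Efficacy Follow-up and is asked again. A site that follows Table 1 to the letter therefore has a planned occasion to learn of a late SAE in one group and none in the other.

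Safety and tolerability, compared between arms, is a secondary objective. The drugs are checkpoint inhibitors, for which the protocol itself expects some events well after the last dose. At stake is the completeness of the post-treatment SAE count. Any distortion of the comparison between arms would need a further condition, taken up below.

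**Working it through.** The plan states no figure for this point, so there is none to reproduce. The check sets the schedules side by side, counts days, and then gives a sensitivity range on assumed inputs.

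**1. The two schedules**

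| | Table 1 (initial treatment) | Table 2 (Second Course) |
|---|---|---|
| SAE window in the note | 90 days, or 30 with new therapy | the same |
| Visit columns | 11 | 10 |
| Columns marked in the AE row | 10 | 10 |
| Survival Follow-up | blank | marked |

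**2. Days after last dose, progression without new therapy**

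- Safety Follow-up Visit: day 30, window +14 (Table 1), so day 30 to 44.
- First survival contact: 12 weeks after the later of the Discontinuation and Safety Follow-up Visits (Section 8.11.5.3), window ±14. Counted from Safety Follow-up, the nominal day is 30 + 84 = 114. The range is 30 + 84 − 14 = 100 to 44 + 84 + 14 = 142.
- With the safety visit at day 30, days without a scheduled check: 90 − 30 = 60, and 60/90 = 67% of the window.

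The next contact always falls after day 90 and carries no AE item.

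**3. Comparison groups**

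- *Efficacy Follow-up.* Table 1 does not say what the 12 weeks are counted from. From a discontinuation visit at day 0, the first visit is at 84 ± 7, so day 77 to 91. From Safety Follow-up, it is at 30 + 84 − 7 = 107 to 44 + 84 + 7 = 135. Either way AE/SAE monitoring is marked there and can look back.
- *New therapy started.* The window closes at day 30, so no gap arises.

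**4. Possible size (all inputs assumed)**

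Let r be the risk of an SAE in days 31 to 90, p the share of the arm stopping for progression, q the share of those with no new therapy, and m the share of their late SAEs missed for want of a question.

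Missed share of the arm = r × p × q × m. Difference between arms = r × q × m × (p₂ − p₁), if r, q and m are equal in both arms.

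| Assumptions | Missed, p = 60% | Difference, p = 50% vs 60% |
|---|---|---|
| r 5%, q 30%, m 25% | 0.05 × 0.60 × 0.30 × 0.25 = 0.2% | 0.05 × 0.30 × 0.25 × 0.10 = 0.04 points |
| r 10%, q 30%, m 50% | 0.10 × 0.60 × 0.30 × 0.50 = 0.9% | 0.10 × 0.30 × 0.50 × 0.10 = 0.15 points |
| r 10%, q 70%, m 50% | 0.10 × 0.60 × 0.70 × 0.50 = 2.1% | 0.10 × 0.70 × 0.50 × 0.10 = 0.35 points |
| r 15%, q 70%, m 100% | 0.15 × 0.60 × 0.70 × 1.00 = 6.3% | 0.15 × 0.70 × 1.00 × 0.10 = 1.05 points |

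With p equal in both arms the difference is zero. If the 1264 enrolled split evenly, there are 632 per arm. The extremes are then 632 × 0.00225 ≈ 1 and 632 × 0.063 ≈ 40 participants per arm with a missed late SAE.

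**The case against.** **Other routes capture these events.** The Synopsis says all participants are followed for SAEs after treatment. Section 4.1 says AE monitoring is ongoing. Section 8.4.1 and Table 7 require every SAE in the window to be reported, whatever the reason for stopping. Section 8.10 requires hospital admissions and emergency visits to be recorded over the same window, and admission is itself an SAE criterion. Deaths come in through survival status. This stands, and it is why the point is a risk and not a prescribed omission. But none of these provisions names a contact after day 30 at which this group is asked. Section 8.4.2 prefers verbal questioning as the way to detect events, and proactive follow-up under Section 8.4.3 starts only after an initial report. The concomitant-medication row of Table 1 stops at the same column.

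**Amendment 06 makes it historical.** In part. Survival contacts have ended, so a mark at that contact alone changes nothing now. But participants leave the study after the safety visit, and Section 8.4.1 does not oblige investigators to look for events in former participants. The amendment still asks for monitoring through a period that runs to day 90 for SAEs. The mismatch remains in the current text, and selected safety analyses will use data gathered under Table 1.

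**Cell positions in extracted tables can shift.** This is a fair caution: the thyroid row of Table 1 does not fit its own note. Here, however, there are ten marks for eleven columns, and the two rows below are marked at Survival Follow-up. Table 2 could be the misprinted one, and the two would still need reconciling.

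**A stronger reading.** A reader might infer that SAEs are ascertained by reason for stopping and that the arm comparison is therefore biased. The documents do not support that. Only the scheduled prompt differs, not the reporting duty. Routing is identical in both arms, and no rates of stopping for progression without new therapy are given. Section 9.6.2 provides only point estimates by arm for the overall SAE summary and treats its safety intervals as descriptive, so no formal test is affected.

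**Conclusion.** The point holds for participants who stop for progression and start no new anticancer therapy. They have no scheduled SAE check for about days 31 to 90, while Table 2 and the Efficacy Follow-up route provide one under the same rule. It does not hold for those who start new therapy, whose window closes at day 30.

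That the schedules disagree does not depend on any assumption. The consequence is a risk of under-ascertaining late SAEs. Its size depends wholly on inputs the documents do not give: 0.2% to 6.3% of an arm across the assumed range, with the top figure requiring every such event to be missed. A between-arm distortion is conditional: zero if the arms have equal shares stopping for progression without new therapy, and 0.04 to 1.05 points if progression stops are 50% versus 60%. Any such distortion is probably small, but the inconsistency is cheap to remove and should be removed.

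**What to change.** 1. Reconcile Table 1 with Table 2, Section 8.4.1 and Section 8.11.5.3. Mark an SAE enquiry at the first contact after the Safety Follow-up Visit, and state in Section 8.11.5.3 that it looks back over days 31 to 90 for participants without new therapy. The look-back must be explicit because that contact falls at day 100 to 142. It already records subsequent therapy, which decides whether the 30-day or 90-day window applies.
2. Reconcile the Amendment 06 bullets. The final visit at Safety Follow-up, the end of survival contacts and monitoring through the Section 8.4 period need one consistent reading, under which each remaining participant without new therapy has a documented SAE enquiry covering the window to day 90.
3. For data already collected, state in the study report how SAEs in days 31 to 90 were ascertained, and show SAEs within 30 days of last dose by arm alongside the full-window count.

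The cost is one schedule mark, a few sentences and a few minutes per participant. Remaining participants also need a brief contact, since survival contacts have ended. The reported SAE count may rise slightly.

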### 1.3.2 Second Course Treatment Phase

Table 2 Study Schedule of Activities – Second Course Treatment Phase

Study Period:	Treatment Cycle = 21 days						End of Treatment	Post-Treatment			Notes
Visit Timing / Cycle Number	1	2	3	4	5	6 to 17	At DC	Safety Follow-up	Efficacy Follow-up	Survival Follow-up	Procedures within a given treatment visit should occur on Day 1 of each cycle unless otherwise noted.
								30 days post last dose	Every 12 weeks post-DC	Every 12 weeks	
Scheduling Window (Days):									+14	±7	
Administrative Procedures											
Eligibility Criteria	X										
Concomitant Medication Review	X	X	X	X	X	X	X	X			Concomitant medications received within 30 days before the first dose of study intervention in the Second Course through 30 days after the last dose of study intervention (or 90 days if used to treat an SAE) will be recorded.
Clinical Procedures/Assessments											
Review Adverse Events	X	X	X	X	X	X	X	X	X	X	Report AEs occurring within 30 days after the last dose of study intervention. Report SAEs occurring within 90 days after the last dose of study intervention, or 30 days after the last dose of study intervention if a new anticancer therapy is initiated, whichever is earlier.
Complete Physical Examination	X						X				
Directed Physical Examination		X	X	X	X	X		X			
Vital Signs and Weight	X	X	X	X	X	X	X	X			Pre-dose and if clinically indicated.

Study Period:	Treatment Cycle = 21 days						End of Treatment	Post-Treatment			Notes
	1	2	3	4	5	6 to 17	At DC	Safety Follow-up	Efficacy Follow-up	Survival Follow-up	
Visit Timing / Cycle Number								30 days post last dose	Every 12 weeks post-DC	Every 12 weeks	Procedures within a given treatment visit should occur on Day 1 of each cycle unless otherwise noted.
Scheduling Window (Days):		±3	±3	±3	±3	±3		+14	±7	±14	
ECOG Performance Status	X	X	X	X	X	X	X				Performed within 7 days of beginning of C1 and prior to each treatment administration.
Study Intervention Administration	X	X	X	X	X	X					
Poststudy Anticancer Therapy Status							X	X	X	X	
Survival Status	←-----→									X	Refer to Sections 8.11.5.3 & 8.11.6. Updated survival status may be requested by the Sponsor at any time during the course of the study.
Laboratory Procedures/Assessments											
Pregnancy Test for WOCBP	X	X	X	X	X	X	X	X			WOCBP require negative serum test within 72 hours or negative urine test within 24 hours prior to each dose of study intervention.
PT/INR and aPTT/PTT	X										Required at C1. Additional testing as needed for participants on anticoagulation therapy.
CBC with Differential	X	X	X	X	X	X	X	X			Performed locally within 10 days before first dose. After C1, collect within 3 days before dosing. Urinalysis should be performed every 4 cycles (C1, C5, etc.).
Chemistry Panel	X	X	X	X	X	X	X	X			
Urinalysis	X				X	X	X	X			
Thyroid function (T3, T4, and TSH)	X	X		X		X		X			Should be performed at C1 and Day 1 of every other cycle starting from C2. Participants may be dosed in subsequent cycles after C1 while thyroid function tests are pending. Free T3 and free T4 are acceptable.

## 2 INTRODUCTION

MK-7684A is a coformulation of MK-7684 and pembrolizumab. MK-7684 is a humanized, antagonist mAb that binds to the immune checkpoint receptor, TIGIT, and blocks the interaction between TIGIT and its ligands. Pembrolizumab is a potent humanized IgG4 mAb with high specificity of binding to the PD-1 receptor, thus inhibiting its interaction with PD-L1 and PD-L2. The coformulation of MK-7684A is being developed as a cancer immunotherapeutic with the potential to be used to increase benefit to patients with metastatic NSCLC.

### 2.1 Study Rationale

The global incidence of lung cancer was 2.1 million cases in 2018, resulting in an estimated 1.8 million deaths [International Agency for Research on Cancer 2018]. NSCLC represents approximately 85% of all lung cancers [National Cancer Institute 2020]. Of patients with NSCLC, tumor histology is approximately 46% adenocarcinoma, 16% squamous, and the remainder “not otherwise specified” [Sulpher, J. A., et al 2013], though histology varies somewhat by geographic region. At the time of diagnosis, approximately 80% of patients in the US with lung cancer have locally advanced or metastatic disease that is not amenable to surgical resection, and the 5-year relative survival for patients with metastatic lung cancer is only approximately 6% [National Cancer Institute 2020a].

The therapeutic landscape in metastatic NSCLC was dramatically changed with approvals of immunotherapy agents, particularly immune checkpoint inhibitors targeting the PD-1/PD-L1 pathway (pembrolizumab, nivolumab, and atezolizumab) for both treatment-naïve and previously treated disease, irrespective of histology. KEYNOTE-024 and KEYNOTE-042 established pembrolizumab monotherapy as first-line therapy for patients with metastatic NSCLC whose tumors express PD-L1 with a TPS  $\geq 50\%$  or (in some countries) TPS  $\geq 1\%$ , respectively, with no *EGFR* or *ALK* genomic tumor aberrations [Brahmer, J. R., et al 2017] [Mok, T. S. K., et al 2019]. Likewise, the positive results from KEYNOTE-189 and KEYNOTE-407 led to the approval of pembrolizumab in combination with pemetrexed and platinum chemotherapy for first-line treatment of patients with metastatic nonsquamous NSCLC whose tumors have no *EGFR* or *ALK* genomic tumor aberrations and pembrolizumab in combination with carboplatin and paclitaxel/nab-paclitaxel for first-line treatment of patients with metastatic squamous NSCLC [Gandhi, L., et al 2018] [Gandhi, L., et al 2018a] [Gandhi, L., et al 2018b] [Paz-Ares, L., et al 2018]. (See Section 2.2.3.2 for details on the results of these studies.)

Despite the significant progress made with the introduction of checkpoint inhibitors either as monotherapy or in combination with chemotherapy, most patients with metastatic NSCLC will still succumb to the disease within 3 years of their diagnosis [Smyth, M. J., et al 2016] [Kruger, S., et al 2019] [Martins, F., et al 2019]. Therefore, there is still substantial unmet medical need for novel therapies that can potentiate the clinical benefit of IO therapies, extend the benefit to a broader population of patients, and further improve treatment response and survival in patients with metastatic NSCLC; of particular interest to both patients and physicians is the development of chemotherapy-free options in biomarker selected patient population.

Thus far, the therapeutic benefit of immunotherapy was largely achieved by blocking the inhibitory receptors PD-1/PD-L1 or CTLA-4. However, it is believed that concurrent or sequential blockade of novel checkpoints within the intricate immune regulatory network could further improve the efficacy of immunotherapy. Recently, dual immunotherapies (IO/IO) either alone or in combination with chemotherapy have also been approved for the treatment of advanced NSCLC [Hellmann, M. D., et al 2019] [Reck, M., et al 2020]. Several other IO/IO combinations and regimens including PD-1/PD-L1 checkpoint inhibitors are under investigation or have been approved recently.

Enhancing the proven anti-PD-1 immune stimulatory mechanism through a novel mechanism of action is therefore an attractive scientific concept. One avenue for further investigation is the T-cell stimulatory/inhibitory network TIGIT (PVRIG/TACTILE)-CD226 (DNAM1) pathway. Antibody blockade of TIGIT, a T-cell inhibitory receptor within this network, has shown promising activity in preclinical cancer models, as well as in clinical studies. MK-7684 is a humanized IgG1 that blocks the inhibitory checkpoint receptor TIGIT expressed on T cells and NK cells. Preclinical data has demonstrated that anti-mTIGIT antibodies on the mIgG2a backbone (with high affinity Fc $\gamma$ R binding) are more efficacious than anti-mTIGIT antibodies on the IgG1 D265A backbone (without Fc $\gamma$ R binding) as single agents and in combination with mDX400 (anti-mPD-1 antibody) in multiple preclinical tumor models. Therefore, a strong rationale exists to develop anti-PD-1 and anti-TIGIT combination therapies. MK-7684 is being developed in combination with pembrolizumab in advanced solid tumors. Preliminary data for MK-7684-001, a Phase 1 study of MK-7684 as monotherapy or coformulated with pembrolizumab (known as MK-7684A) in advanced solid tumors demonstrates promising activity in PD-1 naïve and PD-1 refractory NSCLC (see Section 2.2.3.1).

Recent data from CITYSCAPE, a Phase 2 double-blind study of anti-TIGIT antibody tiragolumab plus atezolizumab versus placebo plus atezolizumab demonstrated a median PFS and OS of 5.6 months versus 3.9 months and 23.2 months versus 14.5 months, respectively in the ITT population after 2.5 years of median follow-up. The combination of tiragolumab plus atezolizumab reduced the risk of disease worsening or death (PFS) by 38% and improved overall response rates (38.8% vs. 20.6%) compared with atezolizumab alone. This improvement was driven predominantly in the participants with PD-L1 TPS  $\geq$ 50% [F. Hoffmann-La Roche Ltd 2021] [Rodriguez-Abreu, D., et al 2020]. However, TIGIT and PD-1 are co-expressed, and data demonstrate improvements in outcomes in all PD-L1 expression subgroups (see Section 2.2.3.1).

In conclusion, there remains a great unmet need to develop newer, more efficacious, well tolerated therapies for the treatment of patients with metastatic NSCLC. The goal of this study is to enhance the approved anti-PD-1 immune stimulatory mechanism of pembrolizumab monotherapy in patients with TPS  $\geq$ 1% NSCLC through combining it with a novel immune modulatory mechanism of action, blockade of TIGIT. This Phase 3 study is designed to assess the efficacy and safety of MK-7684A versus pembrolizumab monotherapy in participants with NSCLC who are treatment-naïve with a PD-L1 TPS  $\geq$ 1% and PD-L1 TPS  $\geq$ 50%. This is an attractive scientific concept and by achieving the primary endpoint of this study, an improved chemotherapy-free clinical therapeutic approach would be created that would significantly enhance presently available options.

